The primary objective of this proposal is to identifying the neurobiologic substrates of emotion-related behavior in CD individuals. After the initial screening and assessment visit, an fMRI study visit will be scheduled (Figure 4). The study will use a double-blind placebo-controlled design. Prior to the scan, participants will receive either intranasal OT (24 IU) or a placebo (PBO) spray. During the scan, BOLD fMRI data will be acquired while the participants perform a series of stressful and non-stressful mental arithmetic challenges (Dedovic et al., 2005). Performance feedback will be provided by the MIST software in real-time and also by the investigator. Participants will complete three runs of the MIST. Subjective responses (anxiety and craving) will be collected at baseline and immediately after each run of the MIST. Participants will also complete an implicit facial affect recognition task. Since the amygdala may habituate to the stress tasks, the order of the tasks will be counterbalanced. At the end of the study visit, subjects will be debriefed, compensated and discharged.

C3b. Participants

Subjects will be men and women of all racial and ethnic groups aged 18-65. A total of 160 study participants will be recruited: (1) cocaine-dependent individuals (CD, n=80); and (2) healthy control subjects free of major Axis I diagnoses (HC, n=80). Gender differences in the neural correlates of stress have been found in fMRI studies of HC and CD individuals (Li et al., 2005; Potenza et al., 2012), and in amygdala responses to fearful faces following intranasal OT administration (Domes, Heinrichs, Glascher, et al., 2007; Domes et al., 2010). Based on our experience in recruiting CD subjects for clinical studies, we expect that 15-20% of the subjects will be female. Differential recruitment will be used as needed to ensure that 15-20% of the participants in each study

group are female. Groups will also be matched on age, smoking status, and education. On a monthly basis, we will assess the status of each group in terms of core variables and tailor recruitment

Figure 4. Overview of Study Visit Procedures

accordingly. This has worked well in all of our previous clinical research studies.

C3c. Recruitment and Retention

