Preprocessing: Post-acquisition preprocessing and statistical analysis of all of the neuroimaging data will be performed using FEAT (FMRI Expert Analysis Tool) Version 5.98, part of FSL (FMRIB's Software Library, www.fmrib.ox.ac.uk/fsl). Functional magnetic resonance imaging (fMRI) blood oxygen level dependent (BOLD) imaging data will be acquired using a standard multi-slice gradient echo planar imaging sequence (TR=2200 ms, TE=35 ms, 64 x 64 matrix, 3 mm isotropic voxels, 271 volumes). Data will be preprocessed using scripting tools from FMRI Expert Analysis Tool (FEAT) Version 5.98, part of FMRIB's Software Library (FSL; www.fmrib.ox.ac.uk/fsl). First non-brain signal will be removed using FSL's BET brain extraction. Scans will be corrected for motion using FSL's linear registration and scans will be spatially smoothed using a Gaussian kernel of 8 mm FWHM. Since head motion can impact functional connectivity analyses, participants with head motion exceeding 0.2 mm will be excluded from the analyses (Power et al., 2012). The "fsl_motion_correction" scripting tool will be used to identify and scrub motion artifacts from each participant's data (Power et al., 2013). Scans will be spatially co-registered with a standardized anatomical template (Montreal Neurological Institute) using a 12 parameter affine transformation (Rorden et al., 2000). **Analysis:** Functional connectivity will be measured using a PPI based approach (Friston et al., 1997). A customized square wave form representing the task (1 = stress condition and -1 = control condition) and the duration of each condition will be convolved with a double-gamma hemodynamic response function. A mask of the seed region will be made using a 12-mm diameter sphere located in the center of the left amygdala using the MNI coordinates (x, y, z = -22, 0, -22). The transformation parameters described above will also be applied to the mask. For each participant and each run of the MIST, the mean corrected and high pass filtered time series of the BOLD signal in the left amygdala will be extracted and used in a single subject whole brain PPI analysis. The PPI model will include (1) the task vector; (2) the time series of the BOLD signal in the left amygdala; (3) a term representing the positive task x seed interaction; and (4) a term representing the negative task x seed interaction. The first level analysis will generate contrast images of the parameter estimates for each of the four regressors. Since the hypotheses associated with Specific Aim 1 explore increases in amygdala - prefrontal cortical connectivity in response to social stress, the group analysis will focus on the positive interaction term. The contrast images of the parameter estimates of the positive interaction term will be entered into a 2nd-level random effects analysis. Unpaired t-tests will be used to test for the following group differences (Hypothesis 1A: CD-PBO vs. HC-PBO) and (Hypothesis 1B: CD-OT vs. CD-PBO). Analyses will be conducted using FMRIBs Local Analysis of Mixed Effects (FLAME 1). Additional analyses comparing (HC-OT vs. CD-OT) will be conducted using an unpaired t-test and applying the appropriate corrections for multiple tests. We will also conduct an exploratory gender analysis between the CD and HC women in the four groups (Domes, Heinrichs, Glascher, et al., 2007; Domes et al., 2010; Potenza et al., 2012). We anticipate that 15-20% of the subjects in each group will be female (n=6/8 per group). We

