
acknowledge that we may be underpowered to conduct these tests. Since there may be important group differences in regional brain activity during the MIST, a secondary whole brain analysis will be conducted using the contrast of interest (stress-control). Analyses will be conducted using FMRIBs Local Analysis of Mixed Effects (FLAME 1). All group level results will be thresholded at $Z>2.3$ using a corrected cluster threshold of $p=0.05$.

Hypothesis 1C: The CD-OT group will report lower subjective anxiety and craving than the CD-PBO group.

Analysis: A linear mixed effects model containing all serially measured time points will be used to assess the effects of OT versus placebo on each dependent variable. Restricted maximum likelihood (REML; Patterson and Thompson, 1971) methods will be used to estimate the fixed effects and variance components, and baseline values will be used as covariates in the regression models. The dependent variables anxiety and craving will be modeled separately. Within each family of dependent measures, the Type I error rate will be controlled using a post-hoc Bonferroni correction. The statistical analyses will be conducted using SAS 9.3 software (SAS Institute Inc., Cary, NC, USA).

Specific Aim 2: Use an implicit facial affect recognition paradigm to determine the impact of cocaine dependence and oxytocin on amygdala activity in response to fearful faces.

Hypothesis 2A: The CD-PBO group will exhibit greater amygdala activity in response to fearful faces than HC-PBO group.

Hypothesis 2B: Compared with the CD-PBO group, participants in the CD-OT group will exhibit lower amygdala activity in response to fearful faces.

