Power and sample size estimates for Hypotheses 1A and 1B were based on pilot data from the MIST (see Preliminary Studies). Based on these data we expect a between group difference (CD-PBO vs. HC-PBO) in the PPI beta estimate of OFC-amygdala connectivity of $\Delta=3.6$ with a RMSE=4.0 ($d = 0.9$) (Cohen, 1988). Assuming an effect similar to the pilot data, the total effective sample size would be 40 subjects per group to provide 80% power for a between groups study design with a type I error rate of 0.05.

Power and sample size estimates for Hypothesis 1C were based on data from a double-blind placebo controlled pilot study of OT on stress reactivity to the Trier Social Stress Task in CD subjects. Based on these data we expect a between group difference in cocaine craving following the MIST of $\Delta=8.24$ with a RMSE=11.03

($d=0.75$) (Cohen, 1988) and a subjective anxiety difference of $\Delta=1.07$ with a $RMSE=2.20$ ($d=0.49$). As in the oxytocin pilot study, participants will be assessed at five time points (m), with an anticipated intraclass correlation coefficient of 0.78 for both craving and anxiety outcomes ($ICC=0.78$ & 0.79, respectively). The design effect, which accounts for the multiple correlated observation within each subject, is estimated to be 4.12 ($DE= [1+(5-1)0.78]$) (Donner and Klar, 2000). Assuming independent observations and an effect similar to the pilot data for the anxiety response ($d=0.48$), the total effective sample size would be 140 subjects (35 CD and 35 controls per treatment arm) to provide 80% power with a type I error rate of 0.05. In a clustered setting, the sample size is $N_{\text{effective}} = nm/DE$ where n is the number of participants required when m replications within participants are performed after accounting for the design effect (DE). For the study at hand, the total number of participants required is therefore estimated to be $N=135$ ($=140*4/4.12$), As such, our proposed sample size of 160 subjects (40 CD and 40 HC per treatment arm) should provide sufficient statistical power to detect the planned anxiety and craving responses to the MIST. To account for an estimated attrition rate of 45%, we will enroll 210 participants in order to complete 160 scans.

Specific Aim 2

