Education: Individual variability in cognitive skills (mental arithmetic) may impact the perception of the task as stressful or non-stressful. However, the MIST program includes an algorithm that ensures that the performance of each individual remains below 50%. In addition, groups will be matched by years of education. Trauma Loads/Recall Bias: Childhood trauma has been shown to affect corticolimbic responses to aversive social cues and to OT administration (Dannlowski et al., 2012; Fan et al., 2014). Study participants will complete the CTQ. Scores on the CTQ may be used as covariates in the analyses. Since the CTQ is a retrospective self-report assessment it is subject to recall bias. However, the psychometric properties of the CTQ are well established in healthy controls and cocaine-dependent populations. Sex: Sex differences have been found in stress-related corticolimbic brain activity in CD subjects and in amygdala responding in healthy controls (Domes, Heinrichs, Glascher, et al., 2007; Domes et al., 2010; Potenza et al., 2012). In our experience in recruiting CD subjects for similar research studies we anticipate that only 12-15% of the CD participants will be female, and therefore do not anticipate gender effects from washing out any potential group differences. Abstinence and Years of Use: Frequency and recency of drug use have been shown to affect drug craving and neuroregulatory stress systems (Fox et al., 2005). Subjects will be asked to report their patterns of drug use in the 90 days prior to the study visit. If there are significant group differences in these factors, they will be used as covariates in the analyses. Ovarian Hormones: Menstrual cycle phase, estrogen and progesterone levels can have a significant impact on drug seeking and craving (Evans et al., 2002; Feltenstein et al., 2007). In addition, estrogen and progesterone levels may impact OT effects in corticolimbic brain regions (Choleris et al., 2008; Gimbel et al., 2002). In order to determine the impact of these variables on study outcomes, participants will be asked to complete a menstrual history diary and plasma estrogen and progesterone samples will be analyzed.

C3h. Data Management

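### The exploratory Aim 1 gender analysis compares women with women only, so it cannot test whether the diagnosis or oxytocin effect differs by gender

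*Combined protocol and SAP*

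**What the plan says.** In C3f Statistical Methods, the analysis paragraph for Hypotheses 1A and 1B sets out the main comparisons: "Unpaired t-tests will be used to test for the following group differences", namely CD-PBO against HC-PBO (1A) and CD-OT against CD-PBO (1B). It then adds: "We will also conduct an exploratory gender analysis between the CD and HC women in the four groups". On numbers it says "We anticipate that 15-20% of the subjects in each group will be female (n=6/8 per group", and the authors "acknowledge that we may be underpowered to conduct these tests".

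The reason for looking at gender is given in C3b Participants: "Gender differences in the neural correlates of stress have been found in fMRI studies of HC and CD individuals". The same section mentions gender differences in amygdala responses after oxytocin, and C3g Design Considerations repeats the motivation.

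Elsewhere gender is a recruitment target (C3b), a balancing factor in the randomization (Medication Administration) and a design consideration (C3g). None of these places defines a comparison of women with men, a men-only analysis, or an interaction involving gender.

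**The concern.** Whether an effect differs by gender is a question about the difference between two effects: the one in women and the one in men. The planned contrast supplies only the first. The plan's caveat is about low power, but sample size is not the obstacle. Forty women per group would give a precise effect in women and still say nothing about whether it differs from the effect in men.

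The practical risk is in interpretation. With 6-8 women per group, a real effect will often miss significance in women while the full-sample contrast reaches it. Setting those two results side by side invites the conclusion that the effect is absent in women, and the plan has no rule against that reading. The gender question that motivates the analysis would also remain untested.

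**Working it through.** **Inputs.** 40 per group; planning difference 3.6 with RMSE 4.0, so d = 3.6/4.0 = 0.9; type I error 0.05 (Power and Sample Size, Specific Aim 1). Sidedness is not stated; two-sided is assumed. Smaller value for sensitivity: d = 0.49, the plan's anxiety effect in the same section, borrowed only to give a range.

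**The plan's own figure.** 0.15 × 40 = 6 and 0.20 × 40 = 8 women per group, as stated, leaving 34 and 32 men. C3g gives a lower share: "we anticipate that only 12-15% of the CD participants will be female". That is 0.12 × 40 = 4.8 to 0.15 × 40 = 6 per CD group, so 5 per group is also shown.

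**Power within each gender, same true effect in both.** Two-sample noncentral t with noncentrality d × √(n/2) and 2n − 2 df. For 6 women per group: 0.9 × √3 = 1.56 on 10 df. For 8: 0.9 × √4 = 1.80 on 14 df.

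**Discordance** (one gender significant, the other not) = pm(1 − pw) + pw(1 − pm), where pw and pm are the powers in women and men.

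| d | Women / men per group | Power, women | Power, men | Discordance |
|---|---|---|---|---|
| 0.9 | 5 / 35 | 0.241 | 0.960 | 0.738 |
| 0.9 | 6 / 34 | 0.292 | 0.955 | 0.689 |
| 0.9 | 8 / 32 | 0.389 | 0.943 | 0.599 |
| 0.49 | 6 / 34 | 0.120 | 0.512 | 0.509 |
| 0.49 | 8 / 32 | 0.150 | 0.488 | 0.492 |

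For 6 women: 0.955 × 0.708 + 0.292 × 0.045 = 0.676 + 0.013 = 0.689.

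The plan contains no men-only test, so the likelier comparison is women against the full sample. In 100,000 simulated trials at d = 0.9, the full sample was significant and the women were not in 69% (6 women) and 59% (8 women).

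**Pooled reading.** The sentence can also mean CD women against HC women across both treatments, with 12-16 women and 68-64 men per diagnosis. At d = 0.9, power in women is 0.559 to 0.693, power in men is above 0.99, and discordance is 0.44 to 0.31.

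**Interaction test.** SE of the difference between the female and male effects, in SD units, is √(2/nw + 2/nm), with 80 − 4 = 76 df.

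- 6 women: √(2/6 + 2/34) = 0.626. 8 women: √(2/8 + 2/32) = 0.559.
- Women-only SE, √(2/nw): 0.577 and 0.500, on 10 and 14 df.
- 95% CI half-width: 1.25 and 1.11 SD for the interaction; 1.29 and 1.07 SD for the women-only contrast. The extra df roughly offset the larger SE.
- Simulated false-positive rate when the effect is equal in both genders: 4.8-5.1%.
- Power for an interaction of 0.9 SD: 29% (6 women) to 36% (8 women). Smallest interaction detectable with 80% power, (1.96 + 0.84) × SE: 1.75 to 1.57 SD.

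**The case against.** The analysis is labelled exploratory, the plan concedes it may be underpowered, and no hypothesis in either aim concerns gender. An estimate within women is a legitimate descriptive target. All of that stands, and it limits the weight of the point. But the caveats are about precision and do not supply a comparison between genders.

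A reader might infer that the women-only test will by itself often signal a gender difference that is not there. The document does not support that. The test keeps its own 5% error rate, and the plan does not propose to conclude anything from setting it beside another result. The discordance figures apply only if someone makes that comparison.

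A reader might also take the chance of missing a real effect in women (1 − 0.292 = 71% to 1 − 0.389 = 61%) as the rate of false gender findings. That is the type II error of one test, and it holds only if treatments are analysed separately. On the pooled reading it falls to 44-31%.

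Read literally, the sentence does not specify an oxytocin-versus-placebo comparison among CD women. If one is intended, it still includes no men.

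Finally, the interaction test is weak too, and a non-significant interaction would not show that the effects are equal. That stands and must be disclosed.

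**Conclusion.** The point holds as a mismatch between question and contrast. As written, the analysis gives an effect within women and leaves the gender question untested, regardless of the number of women.

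If the women's result is read against the men's and the true effect is equal at d = 0.9, the two would disagree on significance about 60-69% of the time with 6-8 women per group, or 31-44% with treatments pooled. An interaction test would give a false signal 5% of the time in the same case. At d = 0.49 with 6-8 women per group the discordance is about 50%.

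The figures assume a two-sided 0.05 test on a single regional estimate with equal variances and no motion exclusions. The planned analysis is whole-brain and cluster-corrected, with participants excluded for head motion above 0.2 mm, so they indicate scale and are not the operating characteristics of the planned test. No primary hypothesis is affected, and the point is minor.

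**What to change.** In the Hypotheses 1A/1B analysis paragraph of C3f Statistical Methods, test gender in the full-sample FLAME 1 model by adding a sex main effect and a group-by-sex interaction. Do this for CD-PBO against HC-PBO and for CD-OT against CD-PBO, using all analysable participants. Report the female effect, the male effect and the interaction from that model with confidence intervals, labelled exploratory. State that no gender difference will be inferred from a women-only result. Reconcile the 15-20% and 12-15% female shares at the same time.

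The cost is two added regressors and their contrasts in each model, with no new data. The estimate for women is kept: from the full model its 95% half-width is about 1.99 × 0.577 = 1.15 SD (6 women) to 1.99 × 0.500 = 1.00 SD (8 women), slightly narrower than the women-only analysis gives. Two limits should be written into the plan. The interaction is imprecise (SE about 0.56-0.63 SD; 29-36% power for an interaction of 0.9 SD), so a null result is not evidence of equal effects. The model also assumes a common variance across sexes.

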Specific Aim 1: To determine the impact of cocaine dependence and oxytocin on functional connectivity between corticolimbic brain regions during acute social stress. Psychophysiological interaction (PPI) analysis using the amygdala as the seed region will be used to assess significant task (stress condition > control condition) x seed interactions. Subjective anxiety and craving data will be collected at baseline and after each run of the MIST.

Hypothesis 1A: The HC-PBO group will exhibit greater functional connectivity between the amygdala and prefrontal cortical regions (orbitofrontal and anterior cingulate cortices) than the CD-PBO group.

Hypothesis 1B: The CD-OT group will exhibit greater functional connectivity between the amygdala and prefrontal cortical regions (orbitofrontal and anterior cingulate cortices) than the CD-PBO group.

Hypothesis 1C: The CD-OT group will report lower subjective anxiety and craving than the CD-PBO group.

Specific Aim 2: Use an implicit facial affect recognition paradigm to determine the impact of cocaine dependence and oxytocin on amygdala activity in response to fearful faces. The BOLD signal measured during neutral faces will be subtracted from the BOLD signal measured during fearful faces.

Hypothesis 2A: The CD-PBO group will exhibit greater amygdala activity in response to fearful faces than HC-PBO group.

Hypothesis 2B: Compared with the CD-PBO group, participants in the CD-OT group will exhibit lower amygdala activity in response to fearful faces.

Currently there are no FDA approved medications for the treatment of cocaine dependence. Identifying the neurobiologic substrates of emotion-related behavior in cocaine-dependent individuals may help in the identification of targets for the development of treatment strategies aimed at controlling emotion-related behavior.

RESEARCH STRATEGY

A. SIGNIFICANCE

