Data Analysis: Following preprocessing (described above), within-task data from individual participants will be analyzed with a fixed-effects general linear model (GLM), with each emotion (described below) modeled as a box-car function convolved with a double-gamma hemodynamic response function. The response period at the end of each block will also be modeled as a separate variable to remove effects of explicit decision making and response selection. The GLM procedure is repeated for each voxel with six movement parameters (3 rotation values in radian and 3 translation values in millimeter) included as covariates to control for the influence of head motion on the data. Following first-level analysis, subject-specific contrasts will be entered into second-level, random-effects analyses. Since the hypotheses associated with Specific Aim 2 explore amygdala activity, we will use a region of interest approach (ROI). The BOLD signal from the left amygdala will be extracted using an anatomical mask generated by a 12-mm diameter sphere located in the center of the left amygdala using the MNI coordinates (x, y, z = -22, 0, -22). The percent signal change between the fearful and neutral conditions (contrast of interest) will be calculated for each participant. Separate random-effects one-way analysis of variance tests (ANOVA) will be used to test for the following group differences (Hypothesis 2A: CD-PBO vs. HC-PBO) and (Hypothesis 2B: CD-PBO vs. CD-OT). Since human neuroimaging studies have found that other brain regions play a role in implicit emotional processing, including the right amygdala and insula (Davidson et al., 1999; Shi et al., 2013), secondary analyses will also include these regions. In addition, OT may impact amygdala responding to happy faces (Domes, Heinrichs, Glascher, et al., 2007), therefore group differences in amygdala responding in the happy-neutral contrast may be explored in future analyses. For multiple comparisons that are not part of the hypothesis a priori, the Bonferroni correction will be used. In addition, contrasts of other pertinent baseline characteristics will be performed between groups. If the groups differ significantly on any of these baseline characteristics, the corresponding variables will be used as covariates in the above analyses. The statistical analyses will be conducted using SAS 9.3 software (SAS Institute Inc., Cary, NC, USA).

Power and Sample Size

Specific Aim 1

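### Hypotheses 1A and 1B are powered on a single OFC–amygdala estimate but tested by a voxelwise cluster threshold with no OFC or ACC region defined, so the stated power does not describe the planned test

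*Combined protocol and SAP*

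**What the plan says.** The Specific Aims and section C3f (Statistical Methods) state 1A and 1B as directional claims about named regions. HC-PBO (1A) and CD-OT (1B) are each expected to show "greater functional connectivity between the amygdala and prefrontal cortical regions (orbitofrontal and anterior cingulate cortices) than the CD-PBO group". Section 5.1 lists amygdala–prefrontal connectivity during the MIST first among the primary outcomes.

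The sample size section covers both hypotheses: "Power and sample size estimates for Hypotheses 1A and 1B were based on pilot data from the MIST". Its effect is a single number for the CD-PBO versus HC-PBO difference: "in the PPI beta estimate of OFC-amygdala connectivity of $\Delta=3.6$ with a RMSE=4.0 ($d = 0.9"). From this, with the error rate set at 0.05, it concludes: "the total effective sample size would be 40 subjects per group to provide 80% power for a between groups study design with a type I" (sentence cut short here). It gives no effect size for ACC and none for CD-OT versus CD-PBO.

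The analysis text under Specific Aim 1 describes something else. The left-amygdala time series is "extracted and used in a single subject whole brain PPI analysis". The resulting contrast images enter a second-level random-effects analysis in FLAME 1, with unpaired t-tests for 1A and 1B. The inference rule is: "All group level results will be thresholded at $Z>2.3$ using a corrected cluster threshold of $p=0.05". The only mask described for Aim 1 is the amygdala seed.

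Aim 2 takes the other route: "Since the hypotheses associated with Specific Aim 2 explore amygdala activity, we will use a region of interest approach (ROI").

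**The concern.** A power calculation is informative only for the test it models. The one given models a two-sample comparison of one regional number per participant. The test in the plan asks whether a contiguous set of voxels above Z = 2.3 is larger than a critical size. Its power depends on how far the effect spreads, how smooth the maps are and how large a volume is searched, and the sample size section uses none of these.

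Two practical consequences follow for a primary outcome. First, a thresholded map gives no effect estimate or confidence interval for amygdala–OFC or amygdala–ACC connectivity. Second, there is no decision rule. The plan does not say whether OFC, ACC or both must be positive, or when a cluster counts as one or the other. The pilot shows why this matters: Figure 2 labels a cluster at (-40, 58, 2) as OFC and also assigns it to Brodmann area 10, with no atlas or boundary named. A region label could therefore be settled after the map is seen.

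**Working it through.** **Inputs.** From Power and Sample Size, Specific Aim 1: difference 3.6, RMSE 4.0, so d = 3.6/4.0 = 0.9; 40 per group; type I error 0.05. Sidedness is not stated; two-sided is assumed unless noted.

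**1. The plan's own figure.** n per group = 2(z₀.₉₇₅ + z₀.₈₀)²/d² = 2(1.960 + 0.842)²/0.81 = 19.4, so 20 (21 with the t distribution; 16 one-sided). The stated 40 per group for 80% power is not reproduced. It would match a two-group total of 2 × 20, which fits the word total in that sentence, but the text says per group.

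**2. Power of the single-estimate test at 40 per group.** Noncentrality = d√(n/2) = 0.9 × √20 = 4.025. The normal approximation at alpha 0.05 is Φ(4.025 − 1.960) = 98.1%. With the noncentral t:

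| Two-sided alpha | Use | Power at d = 0.9 | n per group for 80% (normal approx.) |
|---|---|---|---|
| 0.05 | one region | 97.8% | 20 |
| 0.025 | two regions | 95.7% | 24 |
| 0.0125 | two regions × two hypotheses | 92.6% | 28 |

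The effect detectable with 80% power at 40 per group is d ≈ 0.63 at alpha 0.05 and d ≈ 0.70 at 0.025. For an assumed smaller effect of d = 0.5, power is 60% at 0.05 and 48% at 0.025. This matters for ACC and for 1B, where no effect size is given.

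**3. What the planned cluster test would do.** For one voxel with d = 0.9, P(Z > 2.3) = Φ(4.025 − 2.3) = 95.8%. Exceeding 2.3 is not enough, because the cluster must also pass a critical size. The documents do not give the group-level search volume, final map smoothness or effect extent, so no single power figure follows. As an illustration only, smooth three-dimensional Gaussian maps were simulated under these assumptions: 1.5 L search volume, 3 mm voxels, map smoothness 8 to 12 mm FWHM, cluster-forming Z > 2.3, 5% family-wise error, and a spherical effect with peak d = 0.9 at 40 per group. There were 400 null and 200 signal runs per setting, so the simulation error on a power figure is up to about √(0.25/200) = 3.5 points.

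| Effect radius | FWHM 8 mm (critical size 2.1 cm³) | 10 mm (3.4 cm³) | 12 mm (5.1 cm³) |
|---|---|---|---|
| 5 mm | 6.5% | 1% | 1% |
| 8 mm | 47.5% | 11.5% | 5.5% |
| 10 mm | 89.5% | 47.5% | 13% |
| 12 mm | 100% | 93.5% | 68% |
| 15 mm | 100% | 100% | 99.5% |

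With the same peak effect and the same n, power runs from about 1% to 100% as extent and smoothness change.

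**4. Hypothesis against test.** The hypothesis has two regions and a direction. The power basis is one region, one number per person and one contrast. The planned test is voxelwise, with an unstated search region and no rule linking clusters to regions. These three do not match.

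**The case against.** Cluster-corrected voxelwise PPI is a legitimate method. The threshold matches the pilot's, and the pilot did produce a cluster labelled OFC, though within the healthy controls rather than between groups. Aim 2's choice of a regional test does not oblige Aim 1 to follow. The mismatch could also be resolved by confining the cluster test to a prespecified prefrontal volume, or by powering the cluster test itself. All of that stands. It bears on which remedy to choose, not on whether the plan needs one.

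A reader might infer two stronger things that the documents do not support.

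- **That a whole-brain group search is stated.** It is not. The whole-brain wording describes the single-subject PPI and, separately, a secondary stress-minus-control activity analysis. For the PPI group comparison the search region is simply not given. Whole-brain is the likelier reading because no mask is named, but it is an inference.
- **That the planned test has less power than stated, or that the study is underpowered.** Neither is shown. A spatially broad effect would be detected with power well above 80%. On the single-estimate basis, 40 per group is about twice what d = 0.9 requires.

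A fair caution about the remedy also stands. The power section does not say from what volume the pilot beta was taken. Averaging a focal effect over a whole anatomical mask can lower d, and a generic OFC mask might miss the pilot locus.

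**Conclusion.** The point holds as a mismatch between hypothesis, power basis and test. The stated power does not describe the planned analysis of 1A and 1B, and the power of that analysis cannot be determined from the documents. As written, a primary outcome also has no regional estimate, no confidence interval and no rule for calling a cluster OFC or ACC. The defect does not depend on the whole-brain reading, because the search region and the decision rule are unspecified either way.

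A regional test would be well powered at the plan's own effect size: about 96% with two regions at 0.025 each. That figure assumes that d = 0.9 carries over to a mask mean and applies equally to ACC and to the oxytocin contrast, and the documents support neither extension. The simulated cluster figures rest on assumed smoothness, volume and effect shape, and show only how wide the range is.

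**What to change.** Make the primary test of 1A and 1B the mean positive-interaction PPI estimate per participant, extracted from one OFC and one ACC mask. Fix both masks, with atlas and boundaries, before any group map is seen. State explicitly whether the OFC mask includes the pilot locus (-40, 58, 2; BA 10). Compare groups by unpaired t-test at alpha 0.025 per region, report 95% CIs, and say whether one region or both must be positive for the hypothesis to be supported. Keep the Z > 2.3 cluster map as a secondary analysis and state its search volume.

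Restate the power for that test: at 40 per group and d = 0.9, about 98% at alpha 0.05 and 96% at 0.025, with 80% power at 0.025 needing d of about 0.70. Say that no effect size is available for ACC or for the oxytocin contrast in 1B. If error is also to be controlled across the two hypotheses, alpha 0.0125 leaves about 93% at d = 0.9.

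The cost is two mask definitions and an extraction step on data already planned. The downsides are a two-region multiplicity penalty, possible dilution of a focal effect by mask averaging, and secondary status for effects outside the masks.
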